## ii. LIST OF ABBREVIATIONS

Define all unusual or 'technical' terms related to the trial. Add or delete as appropriate to your trial.

Maintain alphabetical order for ease of reference.

AE	Adverse Event
AR	Adverse Reaction
CA	Competent Authority
CAT-PROM	Cataract surgery patient-reported outcome measures
CI	Chief Investigator
CRF	Case Report Form
FES	Fall Efficacy Scale
GCP	Good Clinical Practice
GMP	Good Manufacturing Practice
IB	Investigator Brochure
ICF	Informed Consent Form
IOLs	Intraocular lens
IPR	Intellectual Property Right
ISF	Investigator Site File (This forms part of the TMF)
ISRCTN	International Standard Randomised Controlled Trials Number
LRI	Limbic relaxing incision
MA	Marketing Authorisation
MHRA	Medicines and Healthcare products Regulatory Agency
MS	Member State
NHS R&D	National Health Service Research & Development
NICE	The National Institute for Health and Care Excellence
NIHR	National Institute for Health Research
NIMP	Non-Investigational Medicinal Product
PAHC	Peninsula Allied Health Centre
PI	Principal Investigator
PIC	Participant Identification Centre
PIS	Participant Information Sheet
QA	Quality Assurance
QC	Quality Control
QP	Qualified Person
RCT	Randomised Control Trial
REC	Research Ethics Committee
SAE	Serious Adverse Event
SAR	Serious Adverse Reaction
SDV	Source Data Verification
SOP	Standard Operating Procedure
SSI	Site Specific Information

Vision and balance changes after bilateral implantation of Toric IOLs  
IRAS ID: 286913

SUSAR	Suspected Unexpected Serious Adverse Reaction
TMF	Trial Master File
TMG	Trial Management Group
TSC	Trial Steering Committee
TUG	Timed Up and Go Test
UHP	University Hospitals Plymouth NHS Trust
UOP	University of Plymouth

Vision and balance changes after bilateral implantation of Toric IOLs  
 IRAS ID: 286913

### iii. TRIAL SUMMARY

Trial Title	Vision and balance changes after bilateral implantation of Toric versus non-Toric intraocular lenses in Cataract patients with astigmatism	
Internal ref. no. (or short title)	Vision and balance changes after bilateral implantation of Toric IOLs	
Clinical Phase	Pre and post operation comparison	
Trial Design	Randomised controlled trial	
Trial Participants	Ambulatory adult aged over 50 years with bilateral cataract patients and astigmatism >1.0D awaiting intraocular lens replacement surgery	
Planned Sample Size	140 participants	
Treatment duration	Up to 12 months after first eye surgery	
Follow up duration	12 months after second eye surgery	
Planned Trial Period	3 years	
	Objectives	Outcome Measures
Primary	
 
• Dynamic balance in functional activities
 
	
 
• Centre of mass and head movement by accelerometer in crossing obstacles, turning and stair walking
 

Secondary	
 
• Eye tracking characteristics
 
• Visual function
 
• Risk of fall
 
• Vision related quality of life
 
	
 
• Area of interest (heatmap) and gaze duration by eye tracking (Tobii pro2) during level ground obstacle crossing and stair walking
 
• Duration of Timed up and go test Visual acuity
 
• IOL rotation
 
• Fall efficacy scale and fear of falling
 
• CAT-PROM 5 questionnaire
 

Investigational Medicinal Product(s)	Monofocal Toric and non-Toric intraocular lens	
Formulation, Dose, Route of Administration	Artificial intraocular lens implantation during cataract correction surgery	

Vision and balance changes after bilateral implantation of Toric IOLs  
IRAS ID: 286913

#### iv. FUNDING AND SUPPORT IN KIND

FUNDER(S)	FINANCIAL AND NON FINANCIAL SUPPORT GIVEN

Carl Zeiss Meditec AG [name] (Product Manager Refractive IOL)
 
Carl Zeiss Meditec AG [name] [contact] [contact] [contact] www.zeiss.com/med
	
 
All Zeiss Toric and non-Toric IOLs needed for this project (bilateral eyes of 140 participants plus spare)
 
Research grant to University of Plymouth grant number: RR2 04499/101 for full-time PhD studentship, participant travel subsidy and research conference subsidy
 

#### v. ROLE OF TRIAL SPONSOR AND FUNDER

Carl Zeiss Meditec AG is the trial funder. It funds the study by providing both the Toric and non-Toric monofocal intraocular lenses needed in the cataract correction surgery for all participants in this study and a research grant to the University of Plymouth covering a full-time PhD studentship, travel subsidy for patients' study visits and related expenses required for presentation of this research in conferences. University Hospitals Plymouth NHS Trust (UHP) is the sponsor. The Research and Development (R&D) Office of UHP provides support for research approval process and implementation to ensure it is compliant to the Health Research Authority (HRA) guidelines. The Consultant Ophthalmologist [name] of UHP provides collaboration as Principal Investigator to lead and provide intraocular lens replacement surgery to selected Cataract patients, as well as review of data analysis and report of result. UHP also provides research support with input from the R&D team to support the implementation of this project.

#### vi. ROLES AND RESPONSIBILITIES OF TRIAL MANAGEMENT COMMITTEES/GROUPS & INDIVIDUALS

The University of Plymouth (UoP) is the provider of the PhD studentship and the related training. The supervisory team holds weekly meetings with the PhD student [name] to monitor the study progress and to discuss any issues arise. The PhD student, the supervisory team, PI and study Sponsor also has regular meeting to update progress of the study and to discuss any issue that impact on the research

Vision and balance changes after bilateral implantation of Toric IOLs  
IRAS ID: 286913

project. The study is also required to comply with the UoP Research Ethics Policy and the Code of Good Research Practice and Research Data Policy

(<https://www.plymouth.ac.uk/research/governance/research-ethics-policy>).

Ethical approval is not required by the University, but this study is also registered on the Plymouth Ethics Online System of University of Plymouth for record purpose.

intraocular lens, dynamic stability, quality of life, eye tracking, visual  
functions, randomised controlled trial

Vision and balance changes after bilateral implantation of Toric IOLs  
IRAS ID: 286913

## ix. TRIAL FLOW CHART

Vision and balance changes after bilateral implantation of Toric IOLs  
IRAS ID: 286913

## 1. BACKGROUND

Cataracts are the most common cause of low vision and blindness in the world (Brian and Taylor, 2001). Cataracts occur when the crystalline lens becomes cloudy preventing light from reaching the retina and so resulting in poor vision. Cataract is highly treatable and the surgery involves removing the cloudy crystalline lens and replacing it with a clear artificial plastic lens (made of acrylic) called an Intraocular lens (IOLs) (Foster, 2001).

Around one fifth of people attending for cataract surgery have astigmatism (Swampillai *et al.*, 2020). Astigmatism refers to the imperfection in the curvature of the cornea, the clear and dome-shaped covering in front of the eye. An eye with severe astigmatism is oval (like a rugby ball) instead of round like a football. This oval shape reduces vision and make vision blurry all over, not just close-up, or far away. While most astigmatism orientated with the steep curve vertically, for some, it can be horizontal (the rugby ball on its side) or more rarely, obliquely positioned (neither horizontal nor vertical). Degree of astigmatism is measured in dioptre (D). A perfect eye has zero dioptre. Most people can have between 0.5-0.75 D and people with 1.5D or more typically need to wear contact lenses or eyeglasses for clear vision.

Conventional non-Toric monofocal IOLs is the most common implants used in cataract replacement surgery. They stay focused at one fixed distance and when chosen to correct distance vision error such as short-sightedness, reading glasses may be needed to see thing close-up. Also, these lenses do not correct astigmatism. In most NHS hospitals such as in UHP, astigmatism often is left untreated during the cataract replacement surgery.

With the advance of IOLs, a modern design of intraocular lenses called Toric IOLs, can correct the astigmatism at the time of cataract replacement surgery. They provide superior correction of astigmatism than other surgical procedures and are known to reduce the need for the patient to wear spectacles after the surgery. Although Toric IOLs may be regarded as “premium IOLs” due to higher cost than conventional Monofocal IOLs, a cost-effectiveness analysis based on hypothetical model in four European countries noted that Toric IOLs were a cost-saving alternative to conventional Monofocal lenses (Laurendeau *et al.*, 2009). The additional vision improvement by correcting astigmatism, especially in older population not only reduce spectacle dependency, but it may also have positive

Vision and balance changes after bilateral implantation of Toric IOLs  
IRAS ID: 286913

impact on balance during daily mobility, reduce fall risk and improve overall quality of life. The purpose of this study is to compare the changes in dynamic balance and vision functions during daily activities among patients with cataract replacement with Toric monofocal IOLs versus those with non-Toric monofocal IOLs.

## 2. RATIONALE

Cataract is one of the major causes of visual impairment and blindness in the aging population. In UK, cataract alone accounts for over a third of the cases of vision impairment in those over 75 years. The Royal College of Ophthalmologists estimated a growth in prevalent cataracts by 43-57% between 2015 and 2035, causing around 50% increase in the expected number of cataract operations over the next 20 years. During cataract correction surgery, artificial lenses, otherwise known as intraocular lenses (IOLs), are used to replace the natural crystalline lens within the eye. By selecting IOLs of appropriate lens power, the pre-existing refractive error of the eye such as short-sightedness can be corrected during the IOLs implantation (Asbell *et al.*, 2005). Routine pre-operation assessment by ophthalmologists usually takes place 2-4 week before the cataract surgery. The ophthalmologist will select the appropriate IOLs by measuring of the axial length of the eye and the curvature of the cornea- the front clear covering of the eye. Implantation of the standard monofocal IOLs can only correct spherical refractive errors (near or far eyesight). Any preoperative astigmatism- imperfection of cornea curvature, can still affect the visual acuity and spectacle dependence after the operation.

Astigmatism is measured in the unit called dioptres (D). People with 1.5D or more usually need to wear contact lenses or spectacles for clear vision. Around 19-22% of the total population has over 1.50DC of corneal astigmatism at the time of cataract surgery (Swampillai *et al.*, 2020). A UK study of 1230 eyes in an NHS cataract clinic even reported about 40% of the patients attending routine cataract surgery had more than 1.00D astigmatism (Khan and Muhtaseb, 2011). It is estimated that patients are 34 times more likely to use spectacles per dioptre of astigmatic error in the better eye (Wilkins *et al.*, 2009). Uncorrected astigmatism not only increases spectacle dependence, even of relatively small amount, it can also result in reduction of visual performance (Read *et al.*, 2014). Reduced vision has been shown to link with poor balance or mobility (Lord, 2006) (Lord *et al.*, 2010) (Black and Wood, 2005). Oblique astigmatism (where the principal meridians are not orientated vertically or horizontally) also proved to affect balance and alter foot placement on steps (Johnson *et al.*, 2013). This could then

Vision and balance changes after bilateral implantation of Toric IOLs  
IRAS ID: 286913

increase the risk of falls and adversely affects the overall economic costs of the cataract surgery and healthcare. Full correction of refractive error including astigmatism may have greater impact on everyday life than previously thought.

In the UK, almost all patients undergoing cataract surgery by the NHS are given monofocal intraocular lenses (IOLs) whether they have astigmatism or not. The National Institute for Health and Care Excellence (NICE) adult cataract management guideline 2017 recommended monofocal IOLs to be used for cataract surgery and only specified not to offer multifocal intraocular lenses for people having cataract surgery (in the NHS). Multifocal IOLs have areas with different focusing power which allows near and distant objects to be seen without the need for spectacles. On the evidence of effectiveness, NICE commented that multifocal IOLs “can provide good near and distance vision without the need for spectacles, but this is at the expense of a variety of potential visual disturbances.” Another systematic review also noted that there was no difference in distance vision between multifocal and monofocal IOLs; but multifocal IOLs had significantly worse results for glare and halos (Khandelwal *et al.*, 2019). Therefore, Monofocal IOLs are the standard IOLs used in NHS. However, there are no recommendations around lens design and material for further consideration.

Toric IOLs, a modern design of intraocular lenses, can provide predictable and precise correction of astigmatism with improvement in vision without spectacles for cataract patients (Kessel *et al.*, 2016). However, prices for Toric IOLs are higher and buying larger volume of the same standard monofocal IOLs is often more economical for the NHS. Therefore, Toric IOLs are not often offered in routine cataract surgery. Although the latest NICE cataract pathways 2021 have added a remark “Please note: the recommendations around lens design and material have been removed to allow for further consideration,” to give surgeon or local NHS Clinical Commission Group (CCG) more freedom to decide on the types of IOLS provision, but there is still insufficient evidence for consistent patient selection criteria. To date, no study has explored the additional effect of correcting astigmatism at the time of cataract surgery, on lifestyle activities and mobility. The purpose of this study is to evaluate the benefits of correcting astigmatism during cataract surgery on an individual's dynamic stability, visual functions, fear of falls and quality of life using modern design Toric IOLs when compared to conventional non-Toric IOLs. The results can provide a more holistic comparison of the two Monofocal IOLs and act as evidence to inform patient selection criteria for Toric IOLs.

Vision and balance changes after bilateral implantation of Toric IOLs  
IRAS ID: 286913

## 2.1 Assessment and management of risk

This study has no higher risk than the risk of standard medical care. However, the study will be considered medium risk: involving an invasive interventional procedure with a low-risk patient population.

### Risks

For Toric IOLs to correct astigmatism, they need to be placed specifically with reference to the steepest meridian of the eye. All IOLs can rotate, but rotation of Toric IOLs can affect its astigmatism correction effect. Small rotations do not affect the astigmatic power, but larger rotations will reduce the astigmatism correcting effect. If the IOL is rotated 30 degrees, the astigmatism correcting effect is eliminated (Visser et al., 2013). In approximately 1% of patients, the Toric lens rotates significantly reducing the level of astigmatism that is corrected by the Toric lens. If this is the case, and the participant is unhappy with their visual outcome, the surgeon will discuss the possibility of a secondary procedure to reposition the lens. The surgeon will discuss the risks of the repositioning procedure with the participant to determine if the benefits outweigh the risks. It is important to note that this repositioning (to correct any unwanted astigmatism) is only possible with Toric lenses, with standard IOLs unwanted astigmatism will not be corrected. Even with significant Toric IOLs rotation, additional surgery is generally not required as by removing the cataract, the rotated Toric IOLs still provide significant improvement in vision and the remaining astigmatism can be corrected with spectacles.

The mobility assessment involves walking over obstacles, turning, going up and down stairs. The participants will have three small portable motion sensors placed on their neck and lower back and will be asked to wear a pair of eye tracking glasses during the mobility tasks. There is a very low risk of falls, similar as during any normal activities of daily living. The risk will be minimal as all assessment will be carried out under the supervision of an experienced physiotherapist. Also, the assessment venues are part of the University campus which is regularly controlled to maintain environmental safety and has provision of first aid equipment. A patient and public involvement discussion has been conducted which covered discussion about assessments and the research design. All participants were supportive about the research idea and felt the research could raise awareness of available choice of IOLs. Participants were asked about the practicality of the research and felt it would be better to have all assessments done in one site. The assessments were to be conducted at Marjon Biomechanics Lab and

Vision and balance changes after bilateral implantation of Toric IOLs  
IRAS ID: 286913

Optometry Lab at PAHC building. This is now changed to the Biomechanics Laboratory at PACH building. There was also discussion about mobility assessments and participants were asked if they felt the tasks were too difficult, risky of fall or too much. All participants felt the mobility task involved were low level and not complicated. They were told that during the mobility assessment, the participant would be required to wear eye tracking glasses and have three movement sensors placed on the body. They felt it was small and light weight and reported no concerns about the additional sensor or glasses.

To assess the eyes comprehensively and take photos, pupil dilating eye drops such as 0.5-1% Tropicamide will be used to dilate the patients' pupils for examination of the back of the eyes. These drops are routinely used in optometry and hospital clinics without need for prescription and all precautions will be taken before administration. The CI, [name] and co-investigator, [name] are registered Optometrist and will carry out this procedure during the study visit at the PAHC. Dilation eye drops may cause blurring of vision and increase sensitivity to bright light. Some people may also experience temporary stinging and dry mouth. The effects of the drops normally last between two and four hours but can be up to six hours. All patients will be reminded on the PIS and by email or telephone contact before the study visits that they must not drive for the appointment and must use alternative means of travel such as taking public transport or ask friend and family to drop them off and collect. They will be advised not to drive or operate heavy machinery until their sight returns to normal and their eyes are comfortable. They will also be advised to wear sunglasses to help reduce light sensitivity after the eyedrop.

As three additional visits are required for the study, there is an increase in number of appointments, but any travel expenses will be reimbursed, and the patients will also have additional care and screening.

As with all studies, there is a very small risk of breach in confidentiality and failure to maintain data securely. Identifiable patient information, in addition to pseudonymised data will be stored at both UHP and UoP, and will be transferred between each site. All data collected will be kept and transferred securely.

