## 4. TRIAL DESIGN

The study is a randomized controlled trial comparing the change of dynamic stability, gaze characteristics, visual function, and quality of life measurements between Toric and non-Toric intraocular lens (IOL) groups.

Vision and balance changes after bilateral implantation of Toric IOLs  
IRAS ID: 286913

The study is a double masked, parallel group design. 140 cataract patients with astigmatism  $>1.0D$  at the Royal Eye Infirmary (REI) of Derriford Hospital will be recruited and randomly assigned to either receive Toric IOLs or non-Toric IOLs for bilateral lens replacement surgery. The randomization will be conducted by the CI who is not involved in the surgical intervention nor the outcome measure assessments. The participants will not know which types of IOLs they are receiving and the study coordinator who assesses the outcome measures will be masked to the types of IOLs given to the participants. Study visits will be carried out before surgery, 3-6 months after first and second eye surgery.

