### **7.3 The randomisation schemes**

The PI will be responsible for recruitment of potential participants from the Cataract clinic at UHP and oversee the consent and eligibility process carried out by the study coordinator. All potential participants will be allocated a unique identification number. The CI, who is independent of the outcome assessments and interventions, will randomize the participants between the intervention and control groups. He will allocate a pseudonymous participant number from 1 to 140. Using simple randomisation with 1:1 allocation ratio through random.org, the 1 to 140 number will be randomly assigned into two groups (Toric IOLs versus non-Toric IOLs). The randomization list will then be passed to the PI, who when recruiting the participants at the pre-surgery clinic can know which type of IOLs (Toric or non-Toric) to prepare for the cataract surgery. At study commencement, each number will be allocated to one of the two groups randomly. This means that subjects are allocated to either arm of the study at the point of recruitment. The randomized list will be held by the PI, who delivers the intervention surgeries. The PI needs to know which lenses are allocated to the patients for surgery purposes but will not participate in the outcome assessment. The study coordinator who is the assessor of the outcome measures will be masked to the allocation of lenses.

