### **7.4 Blinding**

The participants will be masked to the interventions prior to the surgery. They will be told which IOLs they received at the end of their final visit. The CI will conduct the simple randomization for the participants through the random.org and he will be masked to the outcome assessment. The randomized list of participants will be passed to the PI and his ophthalmologist team to prepare the IOLs and deliver the

Vision and balance changes after bilateral implantation of Toric IOLs  
IRAS ID: 286913

cataract correction surgery. So, the PI cannot be masked to the intervention, but he is masked to the outcome assessment.

The outcome assessors for study visits will be masked to the interventions given to the participants. In the post-surgery study visit, the outcome assessors will carry out the dynamic stability reassessment before any visual assessment to ensure they are still masked to the primary outcome measures as the visual assessment will reveal which types of the IOLs the participants received.

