### **7.5 Emergency Unmasking**

During the follow up study visit, if the outcome assessors discover any medical conditions or complications that require further attention, the participants will be referred back to the cataract clinic (for eye complications) or to their GP for any other medical concerns such as acute osteoarthritis needing review of medication. As the study visit takes place at three to six months after the surgery, post-operative complication regarding the IOL implantation or cataract surgery procedure is unlikely. In case it happens, the outcome assessors will be unmasked to the type of interventions received by the patients for further care by asking the patients directly, reviewing discharge summary or contacting CI who holds the randomization list.

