## **14. DISSEMINATION POLICY**

### **14.1 Dissemination policy**

The UHP owns the data arising from the study.

The research data will be recorded pseudonymously. The data collected will then be stored in password protected University MS OneDrive for data analysis.

The data will then be analysed by the CI and co-investigators in its pseudonymous form. No identifiable details will be used in any stage of the analysis.

This project is part of a PhD thesis of the study coordinator. The results in anonymous form will be placed in the thesis for publication on the University's library system (PEARL).

A lay summary of study results will be sent to participants.

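### The Chief Investigator generates the allocation and is said to be apart from outcome assessment, yet is named for study-visit eye procedures and for the data analysis

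*Combined protocol and SAP*

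**What the plan says.** Three sections describe a CI who stays away from assessment. Section 4: "The randomization will be conducted by the CI who is not involved in the surgical intervention nor the outcome measure assessments". Section 7.3: "The CI, who is independent of the outcome assessments and interventions, will randomize the participants between the intervention and control groups". Section 7.4 adds that "he will be masked to the outcome assessment". On the mechanics, Section 7.3 says of the CI: "He will allocate a pseudonymous participant number from 1 to 140". Those numbers are then randomised to the two lens groups.

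Two other sections give the CI work with participants and with outcome data. Section 2.1 (Risks) describes dilating drops given so that the eyes can be fully examined and photographed, and states: "The CI, [name] and co-investigator, [name] are registered Optometrist and will carry out this procedure during the study visit at the PAHC". Section 14.1 states: "The data will then be analysed by the CI and co-investigators in its pseudonymous form".

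The sections disagree on custody of the list. Section 7.3 says: "The randomized list will be held by the PI, who delivers the intervention surgeries". The randomisation row in Section 10.3.1 agrees. Section 7.5, however, gives as one route for emergency unmasking "contacting CI who holds the randomization list".

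The plan has other safeguards. The study coordinator, who assesses outcomes, is to be masked to lens type (Sections 4 and 7.3). Participants learn their lens type only at the end of the final visit (Section 7.4). After surgery, dynamic stability is measured before any visual assessment, because the visual assessment is acknowledged to show which lens was implanted (Section 7.4).

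**The concern.** The usual reason for having someone outside assessment generate the sequence is that the person who knows it then has no chance to influence results. The plan claims that separation and then removes it at two points.

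The first is the study visit. A person who knows the allocation would be working with participants who are meant to stay masked until the end of the third visit, alongside assessors whom Section 5 describes as masked.

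The second is the analysis, and it matters more because it reaches the primary outcome. If the analyst can read the arm from the study number, choices about measures, exclusions and data handling can be made with the arm in view. A report calling the trial double masked, as Section 4 does, would have to disclose both roles.

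**Working it through.** No figure in the plan is at issue, and the sample size is unaffected. The check sets the role statements side by side.

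1. **Does the CI know the arms?** Yes. Under Section 7.3 the CI issues numbers 1 to 140 and randomises them. Section 10.3.1 has the CI generate the list when the study starts. Handing it to the PI does not change this, since no section requires the CI to give up a copy.

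2. **Do pseudonymised data conceal the arm from the CI?** No. Sections 7.6 and 13.7 identify study data by study number, and Section 10.3.1 builds the names of the movement and gaze files from the participant number. The CI's list maps that number to an arm. This assumes that the number on the data is the 1-to-140 number. The documents describe no second code that would break the link.

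3. **Is the CI outside outcome assessment?** Sections 4 and 7.3 say so. Section 2.1 places the CI at the study visit, carrying out dilation for eye examination and photographs. Section 5 has study visits conducted by masked assessors who are optometrists or physiotherapists. The CI is an optometrist with a procedure to perform at the visit and is not masked to allocation. These statements cannot all be true.

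4. **Is the CI masked to the outcomes?** Section 7.4 says the CI is masked to outcome assessment, while Section 14.1 has the CI analyse the outcome data. Nobody can be masked to data that they analyse.

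5. **Does another provision protect the analysis?** None was found. Sections 10.3 to 10.6, 11 and 14.1 specify no masked analyst, no coded arms and no database lock before arm-linked results are seen. There is room for choice: Sections 3.4 and 10.3.2 list angular position, velocity and acceleration, for head and centre of mass, over three activities, without fixing one measure as primary.

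6. **Does the ordering rule in Section 7.4 help?** It protects collection of dynamic stability within a visit. It does not cover later processing or analysis.

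7. **Who holds the list?** Section 7.5 says the CI; Sections 7.3 and 10.3.1 say the PI. By step 1 the CI knows the allocation either way, but the sections still need to agree.

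**The case against.** The strongest reply is that dilation is not outcome measurement. Section 2.1 says the drops are for examining the back of the eye, Sections 3.5 and 3.6 measure lens position with a slit lamp and Pentacam, and Appendix 16.1 treats the drops as a safety task for optometrists. Much of this stands. A reader might infer that the CI grades lens rotation or measures acuity, but no section says so. A reader might equally infer that the CI processes the sensor traces and heat maps. Section 14.1 names the CI and co-investigators jointly, and Sections 10.3.2 and 10.3.3 name software without assigning a person. What survives is that a full eye examination with photographs is more than giving drops, that the CI is present at visits the plan calls masked, and that the reply leaves the analysis role untouched.

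A reader might also infer that the trial's masking as a whole has collapsed. The documents do not support that. Participant masking, the coordinator's masking, and the measurement of dynamic stability before the visual assessment do not depend on the CI. Gaze is recorded during the mobility tasks, the questionnaires are self-administered, and lens rotation is recorded in the Toric group only, so it offers no between-arm comparison to bias. Whether an assessor who does the visual assessment at visit 2 is still masked at visit 3 is a separate question.

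Finally, Section 7.4 concedes that the visual assessment reveals the lens, so anyone doing it may become unmasked. That is correct, and it limits which remedies work.

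**Conclusion.** The contradiction is established. The CI cannot be uninvolved in, independent of and masked to outcome assessment while carrying out an eye procedure at study visits and analysing data whose study numbers the CI randomised. The stated independence fails for the CI. The parts at risk are the eye-visit procedures and the analysis, including the primary analysis.

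On size, all 140 study numbers can be read as arms by the CI. The documents do not say how many visits the CI would attend or how the analysis is divided among investigators, so no estimate of bias is offered. The conclusion assumes that the number on the data is the randomised number and that the CI can still consult the list, which Section 7.5 itself indicates. It does not extend to participant masking or to the coordinator's masking when dynamic stability is collected.

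**What to change.** 1. In Section 2.1, remove the CI from study-visit procedures and assign them to the co-investigator optometrist already named there.
2. In Sections 10.3 and 14.1, state that dynamic-stability and gaze data are processed, and the primary analysis run, on a separate A/B-coded dataset. Leave out the Toric-only rotation data and the refraction data, which would reveal the arm. The people doing this work should be co-investigators who neither know the allocation nor do the visual assessment. The CI sees arm-linked results only after database lock.
3. Make Sections 7.3, 7.4, 7.5 and 10.3.1 name the same list holder.

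Moving the list elsewhere while leaving the CI at the eye examinations would not be enough, because the visual assessment itself shows the lens type.

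The cost is protocol wording and a change to the delegation of tasks, with less flexibility in scheduling eye examinations. No new staff are needed, provided that at least one co-investigator able to run the analysis is outside the visual assessment. The documents do not set out that division of work, so the team should confirm it.
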